2.3 SECONDARY ENDPOINTS

2.3.1 Survival/Mortality

The overall survival rate (the proportion of randomized subjects who survive up to Day 15 and Day 28).

2.3.2 Clinical Improvement

- (Protocol) Time to resolution of fever from randomization up to Day 28 among subjects presenting with Fever (Day 0 fever $\geq 100.4^\circ\text{F}$ / 38.0°C , oral)
- (Protocol) Time to hospitalization/ER visit or death following randomization up to Day 28 (defined as time to disease progression from randomization to either hospitalization/ER visit or death).
- (Protocol) Proportion of subjects with no viral shedding using RT-PCR at Day 7, Day 15, and at early termination.

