8.5 Study Withdrawal, Removal, and Discontinuation of Subjects

Subjects who discontinue study treatment or who are withdrawn from the study for any reason must have the date and the reason for study discontinuation recorded on the electronic case

report form (eCRF). Subjects who discontinue early from the study will be asked to return to the study site within 3 to 7 days of the last administration of study drug to complete assessments as indicated in the Schedule of Assessments ([Table 1](#)) (Early Termination Visit).

In the event that a subject discontinues prematurely from the study because of a TEAE or SAE, the TEAE or SAE will be followed up until it resolves (returns to normal or baseline values) or stabilizes, or until it is judged by the investigator to no longer be clinically significant and thereafter until Day 28.

Upon discontinuation every effort will be made to follow the subjects until Day 28 for all study outcomes unless there is death of the subject, hospitalization, withdrawal of consent by the subject or the subject is lost to follow up.

Once a subject is withdrawn from the study, the subject may not reenter the study.

A subject may voluntarily withdraw or be withdrawn from the study at any time for reasons including, but not limited to, the following:

- AE and/or SAE
- subject withdrawal of consent: at any time, a subject's participation in the study may be terminated at his/her request or on the basis of the investigator's clinical judgment. The reason for subject withdrawal will be noted on the eCRF.
- intercurrent illness: a condition, injury, or disease unrelated to the primary diagnosis that became apparent during treatment and necessitated the subject's termination from the study
- general or specific changes in the subject's condition that renders him/her ineligible for further treatment according to the inclusion/exclusion criteria
- subject fails to adhere to the protocol requirements (e.g., drug noncompliance, failure to return for defined number of visits)
- lost to follow-up: the subject stopped coming for visits, and study personnel were unable to contact the subject
- pregnancy, as indicated in [Section 12.4.5](#).

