3.2 SECONDARY ANALYSIS (PROTOCOL SPECIFIED)

Time to Resolution of fever (existing at day 0): This analysis will be conducted in the subjects with Day 0 temperature $\geq 100.4^{\circ}\text{F} / 38.0^{\circ}\text{C}$. Time to resolution of fever is defined as the time (in days) from initiation of study treatment (active or placebo) until normalization of fever ($< 100.4^{\circ}\text{F} / 38.0^{\circ}\text{C}$ oral) and sustained for at least 72 hours; this will only be assessed in subjects who experienced a fever within 24 hours of enrollment. In the analysis of time to resolution of fever, temperature is recorded everyday up to day 14. Occurrence of fever is recorded as a binary (yes/no) a fever ($\geq 100.4^{\circ}\text{F} / 38.0^{\circ}\text{C}$) was recorded on the following day using the e-diary.

Time to Disease Progression (Hospitalization/ER visit or Death): Defined as time to disease progression from randomization to either COVID-19 related hospitalization/ER visit or death through Day 28. The primary endpoint is a binary endpoint of Disease Progression, this protocol specified analysis captures the temporal occurrence of the event.

Viral shedding (Resolution): Participants will have Viral Shedding characterized and evaluated as having Viral shedding or not having Viral shedding for this secondary endpoint. Viral shedding will be collected using reverse transcriptase-polymerase chain reaction (RT-PCR) at Day 7, Day 15, and at Day 28 or Early Termination. Subjects will have mid-turbinate nasal samples taken using flocked swabs at onsite study visits. The same nostril should be used for sampling each time it is done, and the nostril (right or left) should be recorded on the eCRF. Use of both nostrils is not to be a Major Protocol Deviation and therefore will have no bearing on the analysis populations. Details of collection method and laboratory requirements are defined in the Clinical Protocol.

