4 ANALYSIS APPROACH

4.1 ANALYSIS OF THE PRIMARY EFFICACY ENDPOINT

4.1.1 Primary Efficacy Endpoint

The primary endpoint (the proportion of subjects requiring COVID-19 related hospitalization/ER visit or who died due to any cause within 28 days of randomization) will be analyzed using an unadjusted Pearson chi-squared test. If the expected number of events in either group is less than five (5), a Fisher's exact test will be used.

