4.1.7 Handling of Missing Data for the Primary Efficacy Test

To provide a true ITT efficacy test, subjects lost-to-follow-up prior to Day 28 must be imputed. A multiple imputation (MI) (Rubin and Schenker 1991)³ strategy will be used in the primary efficacy test followed by a completers analysis and a tipping point analysis as sensitivity analyses that examine the robustness of the Missing at Random (MAR) assumption necessary for valid application of MI.

To implement the MI for primary efficacy testing, 20 imputed data sets will be constructed. If the pattern of missing data is not monotonic, a fully conditional (FCS) approach as implemented in SAS PROC MI (SAS Institute)⁴ will be utilized. If the pattern of missing data is monotonic, a regression approach may be used. The MI model will include age, BMI, sex, and the number of days since first COVID-19 symptom (≤ 5 or > 5 days), as well as temperature at Day 7 and 14 taken at the clinic. Should the pattern of missing data be non-monotonic, an FCS model will be utilized. The estimated treatment group difference and standard error will be determined for each imputed data set and combined using Rubin's rule as implemented in SAS PROC MIANALZE. The final treatment group difference will be the average of the multiple imputed datasets. The standard error, p-value, and width of the confidence interval will account for both within and between imputation error.

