4.2.2 Clinical Improvement

Time to resolution of fever from randomization up to Day 28 will be analyzed with Kaplan Meier⁵ survival analyses. A log-rank test will be used to compare this time-to-event outcome between groups. The median event time and their corresponding 2-sided 95% CIs will be provided for each treatment arm. The analysis will treat subjects who die and have not yet had a fever resolve as having their fever having not been resolved at Day 28. A sensitivity analysis of this analytical approach will be performed, and the interpretation discussed in the Clinical Study Report.

Time to COVID-19 related Hospitalization/ER visit or Death (disease progression) will be provided using a similar approach as to time to fever resolution.

If needed, between group comparisons will be made accounting for covariates that may be associated with outcome which clinically significant baseline differences were observed despite randomization as determined by the Sponsor Safety Monitor and Principal Investigator using a proportional hazard (Cox) regression⁶.

Proportion of subjects with no viral shedding (yes/no) using RT-PCR at Day 7, Day 15, and at early termination will be analyzed using the approach specified for the primary endpoint.

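### The SAP extends the primary endpoint's between-arm test to viral shedding at Early Termination, where only early withdrawals have a swab and there is no common study day

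*SAP*

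**What the plan says.** SAP 2.3.2 defines the endpoint as "Proportion of subjects with no viral shedding using RT-PCR at Day 7, Day 15, and at early termination". The instruction to test is in SAP 4.2.2, where the proportion "at early termination will be analyzed using the approach specified for the primary endpoint", as it also will be at Day 7 and Day 15. Under SAP 4.1.1 the primary endpoint "will be analyzed using an unadjusted Pearson chi-squared test", with a fallback: "If the expected number of events in either group is less than five (5), a Fisher's exact test will be used". SAP 4.1.7 adds the missing-data step: "To provide a true ITT efficacy test, subjects lost-to-follow-up prior to Day 28 must be imputed". The table list in the SAP appendix carries Early Termination into Tables 14.2.7.1 to 14.2.7.3, for ITT, PP1 and PP2.

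The protocol says who has the swab and when. Section 6.2.2 limits the Early Termination assessment to subjects withdrawn before finishing the 14-day treatment period, and 7.1 and 7.3 agree. Section 8.5 asks them to return "within 3 to 7 days of the last administration of study drug". Section 13.3.2 lists and analyzes shedding at Day 7 and Day 15 only. SAP section 1 says that the SAP prevails where the two differ.

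SAP 3.2 describes swab collection "at Day 7, Day 15, and at Day 28 or Early Termination". Protocol 10.1.2 makes Day 28 a telephone visit and takes swabs on site only, at Day 7, Day 15 and Early Termination. Table 1 shows no Day 28 swab.

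**The concern.** A between-arm test has its usual meaning when the groups compared are those formed by randomization and are measured at the same time. The Early Termination swab meets neither condition.

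Subjects enter this group by leaving the study. The reasons in Protocol 8.5 include adverse events and non-adherence, which treatment can influence. The day of the swab depends on when the subject stopped. Protocol 5.1.1 notes that viral levels fall over the week after onset, so a later swab is more likely to be negative whatever the treatment.

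The risk is a p-value printed beside the valid Day 7 and Day 15 results as if it carried the same weight. It could show a difference, or hide one, purely through who withdrew and when.

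**Working it through.** **1. Swab day.** A subject withdrawn before completing treatment has a last dose on about Day 1 to Day 13. Adding the 3 to 7 days of Protocol 8.5:

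- earliest: 1 + 3 = Day 4
- latest: 13 + 7 = Day 20

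Table 1 adds a visit window of one day either way. The SAP sections on this endpoint give no rule assigning the swab to a nominal visit and no adjustment for swab day.

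**2. What timing alone can do.** The documents give no clearance rate, so this is an illustration. Assume exponential clearance with median m days and no drug effect. The chance of a negative swab on day t is 1 − 0.5^(t/m).

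| Median m | Day 4 | Day 7 | Day 14 | Day 20 | Day 20 minus Day 4 | Day 14 minus Day 7 |
|---|---|---|---|---|---|---|
| 7 days | 33% | 50% | 75% | 86% | 53 points | 25 points |
| 10 days | 24% | 38% | 62% | 75% | 51 points | 24 points |
| 14 days | 18% | 29% | 50% | 63% | 45 points | 21 points |

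The first difference is the extreme. The second is what would appear if one arm's withdrawals were typically swabbed a week later than the other's.

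**3. How many swabs.** The nearest stated figure is the sample size: 80% power at 186 and 93 (SAP 4.1.4). It reproduces closely. With 15% versus 30%, exact enumeration gives 80.2% for Fisher's test and 78.9% for a continuity-corrected chi-square. The protocol's 183 and 92 give 80.2% by Fisher's test.

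The allowance above those sizes is the only guide to the number leaving:

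- SAP: 200 − 186 = 14 and 100 − 93 = 7, total 21 (21/279 = 7.5%)
- Protocol: 200 − 183 = 17 and 100 − 92 = 8, total 25

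This is an assumption. The SAP's allowance is for loss to follow-up, and a subject who cannot be contacted gives no swab. Withdrawals who do return are not counted anywhere. The true number could be lower or higher.

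**4. Which test would apply.** SAP 4.1.3 states the fallback in terms of expected cell counts below 5. With 7 placebo swabs, the expected negatives and positives sum to 7, so the smaller is at most 3.5. With 8 it is at most 4. The exact branch therefore applies whatever the shedding rates. At least 10 placebo swabs are needed for both cells to reach 5.

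**5. Power of Fisher's test.** Assumed proportions negative, camostat versus placebo; two-sided 0.05; exact enumeration. The last two rows show larger counts.

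| Swabs | 65% vs 50% | 75% vs 50% | 60% vs 30% | Smallest expected cell |
|---|---|---|---|---|
| 14 vs 7 | 5.2% | 12.7% | 15.4% | 2.3 to 3.5 |
| 17 vs 8 | 6.5% | 14.8% | 22.0% | 2.6 to 4.0 |
| 20 vs 10 | 8.7% | 23.1% | 23.6% | 3.3 to 5.0 |
| 30 vs 15 | 12.4% | 32.8% | 39.0% | 5.0 to 7.5 |

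At a low count such as 4 versus 2, significance is impossible: the most extreme table has probability 1/C(6,2) = 1/15 = 0.067.

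**6. PP1.** SAP 2.5.2 admits only subjects who complete the 14-day treatment period. Protocol 6.2.2 gives the Early Termination swab only to those who do not. The two sets do not overlap, so the Early Termination part of Table 14.2.7.2 is empty by construction. SAP 2.5.2 counts an unreturned bottle as all doses taken, but that settles compliance and does not turn a withdrawal into a completer.

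**The case against.** The best defence is that Early Termination belongs to the protocol's own endpoint (6.2.2), so the SAP is right to list and report it. That stands: it should stay in SAP 2.3.2. It does not justify a formal test, because the protocol's analysis section leaves Early Termination out.

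Three stronger readings are tempting, and the documents do not support them.

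- A reader might infer that everyone who completed treatment counts as missing at Early Termination and would be multiply imputed. SAP 4.1.7 is written for the primary test and imputes subjects lost to follow-up before Day 28; a completer who was never due this visit is not one of them. At counts near 14 versus 7 the exact branch would apply, and for that branch SAP 4.1.7 keeps only the tipping point analysis. The actual gap is that no denominator is stated.
- A reader might attach a normal-approximation interval to 14 versus 7. With 50% negative in each arm the half-width is 1.96 × √(0.25/14 + 0.25/7) = 0.45, but that describes a difference near zero, and SAP 4.1.3 switches to exact binomial intervals at such counts.
- A reader might infer that Early Termination swabs are barred from filling Day 7 or Day 15 gaps. The SAP is silent on this. Assigning them by a window is an option, not a correction of a stated rule.

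It is also fair to say that the swab day is not haphazard, since it is tied to the last dose. But that fixes no common day since randomization. The consequence is small: one occasion of one secondary endpoint in a Phase 2 trial.

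**Conclusion.** The point holds. SAP 4.2.2 prescribes a between-arm test in a group selected after randomization and swabbed on no common day, beyond what Protocol 13.3.2 analyzes. These facts come from the documents and need no assumed figure; the same is true of the empty PP1 section and the unscheduled Day 28 swab.

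The size rests on assumptions. If the swabs number about 14 versus 7 or 17 versus 8, power is about 5% to 22% for the negativity rates tried. More swabs would raise the power but would not remove the selection or the timing problem. The 45 to 53 points from timing are an extreme under assumed clearance medians of 7 to 14 days, not a forecast of bias.

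This is a minor point that is easily corrected. The primary analysis, the sample size and the Day 7 and Day 15 comparisons do not change.

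**What to change.** - In SAP 4.2.2, restrict the formal test of shedding to Day 7 and Day 15, in line with Protocol 13.3.2.
- Keep Early Termination in SAP 2.3.2. Report it descriptively by arm, with the number swabbed as the denominator and the swab day shown, and without a p-value. Adapt Tables 14.2.7.1 and 14.2.7.3 accordingly.
- Remove Early Termination from the PP1 table, 14.2.7.2.
- Optionally, assign an Early Termination swab to Day 7 or Day 15 when it falls within a window fixed before unblinding, and list the rest.
- Reconcile the Day 28 wording in SAP 3.2 with Protocol Table 1 and section 10.1.2, which schedule no swab that day.

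The cost is a few lines of SAP text and small changes to the table shells. There is one test fewer, no new data, and no change to sample size or power.

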2.3.3 Safety/Tolerability

- Incidence of AEs and SAEs of any grade from randomization up to Day 28.

- Cumulative incidence of grade 3 and 4 AEs from randomization up to Day 28.
- Incidence of discontinuation from study due to an AE/SAE (discontinued subjects will be followed up until Day 28).
- Change from baseline in clinical laboratory parameters (including platelet counts, liver function tests, and potassium levels, etc.).
- Change from baseline in vital signs (heart rate, blood pressure, peripheral capillary oxygen saturation [SpO₂]).

2.4 RANDOMIZATION

Subjects will be randomized in a 2:1 ratio of Camostat mesilate: placebo. Approximately 300 subjects are planned to be enrolled (200 subjects to Camostat mesilate and 100 subjects to placebo).

One global computer generated, blocked randomization list with 2/3's of the assignments will be to Camostat mesilate and 1/3 to placebo, in random order. Randomization block sizes will randomly vary in size 3 and 6. Labeling will be randomly varied as an additional masking feature.

2.5 ANALYSIS SETS

2.5.1 Intent-to-Treat Population (ITT)

The Intent-to-Treat (ITT) population will include all subjects who are randomized. Subjects will be analyzed according to their study treatment assignment, not according to the treatment actually received. The ITT population is the primary population and will be used for evaluating primary and secondary efficacy endpoints and subject baseline characteristics.

2.5.2 Per-Protocol Population #1 (PP1)

The first Per-Protocol population (PP1) will include all subjects in the ITT population who complete the 14-day treatment period with 80% compliance with drug. Subjects will be analyzed according to the treatment actually received. 80% compliance of drug is determined by counting the number of pills returned at the end of the study. Subjects who do not return a bottle are assumed to have taken all doses. The primary and secondary efficacy endpoints will be evaluated in the PP1 population.

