2.5.3 Per-Protocol Population #2 (PP2)

A second Per-Protocol population (PP2) will include all subjects in the ITT population who do not have major protocol deviations or clinically important intercurrent events thought to confound assessment of primary outcomes. The PP2 population will be provided for primary and secondary efficacy endpoints.

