4.3.8 Compliance of Drug

Subjects are instructed to take 112 of the Camostat mesilate 100 mg/Placebo tablets, 2 tablets, 4 times per day, for 14 days. At the end of the study, subjects will return their bottle and the number of tablets returned will be counted. Subjects who do not return the bottle are assumed to have taken all the tablets, and therefore, return 0.

Exposure to the drug will be characterized as number of tablets taken using descriptive statistics including number of subjects, mean, SD, Q1, median, Q3, minimum and maximum.

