4.7 PROTOCOL DEVIATIONS

The following Protocol Deviations (PD) will be captured for all subjects and recorded in the Protocol Deviation Log. The protocol Deviation log will capture deviations into the buckets

⁷ Viechtbauer W. Bias and efficiency of meta-analytic variance estimators in the random-effects model. *J Educ Behav Stat.* 2005;30(3):261-293.

⁸ Higgins JP, Thompson SG, Deeks JJ, Altman DG. Measuring inconsistency in meta-analyses. *BMJ.* 327(7414):557

shown in the ‘Deviation’ column of the following table. The bucketed deviations will be provided to the Sponsor Study Safety Monitors for review and classification per the Classification system outlined in [Protocol Deviation Classifications](#). If a PD falls out of these categories, they will be handled on a case-by-case basis by sponsor medical monitors.

Table 1: Protocol Deviation Classifications

Deviation	Classification	Note
Required procedure performed incorrectly	Minor if not primary endpoint	
Required procedure not performed	Minor if not primary endpoint	This will not include missing e-diary temperatures. This will be addressed in the section in missing data for secondary endpoint of fever.
Out of window visit	Minor	
Missed Visit/Visit not performed	Minor	The window around the 72 hours from notification of positive COVID is +4 hours. Therefore, if notification occurs up to and including 76 hours, the deviation will be minor, otherwise, Major.
Specimen temperature excursion	Requires case by case via Sponsor	
Study product temperature excursion	Requires case by case via Sponsor	
Study product not stable	Requires case by case via Sponsor	
Blood not collected	Minor	
Nasal swab not collected	Minor	
Did not meet Inclusion/Exclusion criteria	Major	
Informed consent deviations	Major	
Incorrect study drug given per randomization:	Major	
Subject fails to take 80% of study drug	Major	Subject is included in ITT and Safety Population (if at least one dose was taken)

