5 APPENDIX: SHELL TABLES AND FIGURES

This section displays mock-ups of the tables, listings, and figures that will be provided in the clinical study report.

SAP TLF's are provided to describe data presentations including examples of the Tables, Listings, and Figures.

The following is a DRAFT set of Tables, Listings, and Figures. Table numbers, layouts, and units are subject to revision.

Table 2: Listing of Tables, Listings, and Figures

TLF Name	TLF Number	Population
Accounting		
Table 14.1.1 - Subject Disposition by Treatment	Table 14.1.1	ITT
Figure 14.1.1 – Subject Disposition by Treatment – Consort Diagram	Figure 14.1.1	ITT
Baseline Demographics		
Table 14.1.2.1 - Summary of Demographic Characteristics by Treatment	Table 14.1.2.1	ITT
Table 14.1.2.2 - Summary of Demographic Characteristics by Treatment	Table 14.1.2.2	PP1
Table 14.1.2.3 - Summary of Demographic Characteristics by Treatment	Table 14.1.2.3	PP2
Table 14.1.2.4 - Summary of Demographic Characteristics by Treatment	Table 14.1.2.4	SP
Table 14.1.3 - Summary of Baseline Clinical Laboratory Data by Treatment	Table 14.1.3	ITT
Table 14.1.4 - Summary of Baseline Vital Signs by Treatment	Table 14.1.4	ITT
Primary/Secondary		
Table 14.2.1.1 - Primary Efficacy – Proportion of Subjects Requiring COVID-19 Hospitalization/ER visit	Table 14.2.1.1	ITT
Table 14.2.1.2 - Secondary Efficacy – Proportion of Subjects Requiring COVID-19 Hospitalization/ER visit	Table 14.2.1.2	PP1
Table 14.2.1.3 - Secondary Efficacy – Proportion of Subjects Requiring COVID-19 Hospitalization/ER visit	Table 14.2.1.3	PP2
Table 14.2.1.4 – General Linear Model of COVID-19 Hospitalization/ER visit Adjusted by Covariates	Table 14.2.1.4	ITT
Table 14.2.1.5 – General Linear Model of COVID-19 Hospitalization/ER visit Adjusted by Covariates	Table 14.2.1.5	PP1
Table 14.2.1.6 – General Linear Model of COVID-19 Hospitalization/ER visit Adjusted by Covariates	Table 14.2.1.6	PP2
Table 14.2.1.7 – Forest Plots of Group Difference in Primary Endpoint with 95% Confidence Intervals Stratified by Categorical Baseline Characteristics	Table 14.2.1.7	ITT
Table 14.2.1.8 – Forest Plots of Group Difference in Primary Endpoint with 95% Confidence Intervals Stratified by Categorical Baseline Characteristics	Table 14.2.1.8	PP1
Table 14.2.1.9 – Forest Plots of Group Difference in Primary Endpoint with 95% Confidence Intervals Stratified by Categorical Baseline Characteristics	Table 14.2.1.9	PP2

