Table 14.2.2.1 – Counts and Percentages Surviving to Days 15 and 28 Days by Treatment Group in ITT	Table 14.2.2.1	ITT
Table 14.2.2.2 – Counts and Percentages Surviving to Days 15 and 28 Days by Treatment Group in PP1	Table 14.2.2.2	PP1
Table 14.2.2.3 – Counts and Percentages Surviving to Days 15 and 28 Days by Treatment Group in PP2	Table 14.2.2.3	PP2
Table 14.2.3.1 – Time to Resolution of Fever by Treatment in ITT Analysis Set	Table 14.2.3.1	ITT
Table 14.2.3.2 – Time to Resolution of Fever by Treatment in PP1 Analysis Set	Table 14.2.3.2	PP1
Table 14.2.3.3 – Time to Resolution of Fever by Treatment in PP2 Analysis Set	Table 14.2.3.3	PP2
Figure 14.2.4.1 – Kaplan-Meier Time to Resolution of Fever in ITT	Figure 14.2.4.1	ITT
Figure 14.2.4.2 – Kaplan-Meier Time to Resolution of Fever in PP1	Figure 14.2.4.2	PP1
Figure 14.2.4.3 – Kaplan-Meier Time to Resolution of Fever in PP2	Figure 14.2.4.3	PP2
Table 14.2.5.1 – Time to COVID-19 Hospitalization/ER visit or Death by Treatment in ITT	Table 14.2.5.1	ITT
Table 14.2.5.2 – Time to COVID-19 Hospitalization/ER visit or Death by Treatment in PP1	Table 14.2.5.2	PP1

TLF Name	TLF Number	Population
Table 14.2.5.3 – Time to COVID-19 Hospitalization/ER visit or Death by Treatment in PP2	Table 14.2.5.3	PP2
Figure 14.2.6.1 – Kaplan-Meier Time to COVID-19 Hospitalization/ER visit by Treatment in ITT	Figure 14.2.6.1	ITT
Figure 14.2.6.2 – Kaplan-Meier Time to COVID-19 Hospitalization/ER visit by Treatment in PP1	Figure 14.2.6.2	PP1
Figure 14.2.6.3 – Kaplan-Meier Time to COVID-19 Hospitalization/ER visit by Treatment in PP2	Figure 14.2.6.3	PP2
Table 14.2.7.1 – Proportion of Subjects with No Viral Shedding at Days 7, 15, and at Early Termination in ITT	Table 14.2.7.1	ITT
Table 14.2.7.2 – Proportion of Subjects with No Viral Shedding at Days 7, 15, and at Early Termination in PP1	Table 14.2.7.2	PP1
Table 14.2.7.3 – Proportion of Subjects with No Viral Shedding at Days 7, 15, and at Early Termination in PP2	Table 14.2.7.3	PP2
Table 14.2.8.1 – Shift Table of Fever Severity Categories	Table 14.2.8.1	ITT
Table 14.2.8.2 – Shift Table of Fever Severity Categories	Table 14.2.8.2	PP1
Table 14.2.8.3 – Shift Table of Fever Severity Categories	Table 14.2.8.3	PP2
Tables Safety		
Table 14.3.1.1 - Overall Summary of Adverse Events by Treatment	Table 14.3.1.1	SP
Table 14.3.1.2 – Adverse Events Occurring in 5% of Subjects in Either Treatment Group by MedDRA System Organ Class and Preferred Term	Table 14.3.1.2	SP

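### PP1 and PP2 make no exception for dosing ended by a primary event, so PP1 survival to Day 15 is conditioned on its own outcome; an unreturned bottle is scored as full compliance

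*SAP*

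**What the plan says.** The SAP makes ITT the primary population (2.5.1) and repeats the primary and secondary efficacy endpoints in two per-protocol sets.

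- **PP1** (2.5.2) takes ITT subjects "who complete the 14-day treatment period with 80% compliance with drug", measured by pill count. It adds: "Subjects who do not return a bottle are assumed to have taken all doses".
- **PP2** (2.5.3) takes ITT subjects "who do not have major protocol deviations or clinically important intercurrent events thought to confound assessment of primary outcomes". In SAP 4.7, Table 1, the row "Subject fails to take 80% of study drug" is classed as Major, so low compliance removes a subject from PP2.
- **Compliance** (4.3.8): "Subjects are instructed to take 112 of the Camostat mesilate 100 mg/Placebo tablets", and again "Subjects who do not return the bottle are assumed to have taken all the tablets", that is, zero tablets returned.

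The primary endpoint counts COVID-19 related hospitalization, ER visit or any death up to Day 28 (SAP 3.1). The list of outputs in SAP 5 labels the PP1 and PP2 versions of that table "Secondary Efficacy – Proportion of Subjects Requiring COVID-19 Hospitalization/ER visit" and includes "Counts and Percentages Surviving to Days 15 and 28 Days by Treatment Group in PP1". Protocol 11.1 has subjects record in a daily eDiary how many doses they took. None of the PP rules uses those counts.

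**The concern.** A per-protocol rule that depends on finishing treatment can depend on the outcome when the outcome itself can end treatment. Here the event window (28 days) contains the dosing window (14 days), and Protocol 5.1.1 places deterioration most often about a week after symptom onset. Events during dosing are therefore plausible. Whether such an event stops dosing is a different matter, and the documents are silent on it except that death plainly does.

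The ITT result is not at stake. What is at stake is how the PP1 and PP2 tables are read beside it. SAP 4.1.6 says the totality of evidence will inform the Phase III decision, and a reader could take a selection artefact for attenuation of the effect, or for good survival in compliant subjects.

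The bottle rule is a separate defect. It assigns a value that can be known to be false, and it can decide PP2 membership by whether a container came back.

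**Working it through.** **The plan's own figures.** SAP 4.1.3 expects nearly 28 events per arm: 186 × 0.15 = 27.9 and 93 × 0.30 = 27.9, which agrees. The 80% power in SAP 4.1.4 also reproduces: exact enumeration at 186/93 gives 78.9% for the continuity-corrected chi-square and 80.2% for Fisher's test. At the enrolment target of 200/100 the planning rates give 30 events in each arm and 170 and 70 non-events. These counts are used below.

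**Compliance cut-off.** A full course is 2 × 4 × 14 = 112 tablets (SAP 4.3.8). SAP 2.5.2 does not state the denominator; taking 112 is an inference. Then 0.80 × 112 = 89.6 tablets, and 89.6 / 8 = 11.2 days. Dosing that ends before about Day 12 fails the 80% rule (PP2, if the bottle is returned). Dosing that ends at any time before the 14 days are up fails the completion condition (PP1). Events after dosing ends affect neither, so the conditioning is partial.

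**Bottle rule.**
- A subject who dies on Day 3 can have taken at most 3 × 8 = 24 tablets. With no bottle returned, the SAP records 112.
- Two subjects each stop after six full days: 48 / 112 = 43%. The one who returns the bottle has a Major deviation and leaves PP2. The other is scored 112 / 112 = 100% and can stay. In PP1 the completion condition may still exclude the second subject, but the SAP does not say how completion is determined.

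**Effect of selection on PP event rates.** Let f be the share of event subjects excluded and g the share of non-event subjects excluded, equal in both arms. The documents give neither, so both are assumed.

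PP rate = 30(1-f) / [30(1-f) + 170(1-g)] for camostat, with 70 in place of 170 for placebo. ITT truth: 15% vs 30%, difference -15.0 points, risk ratio 0.50.

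| f | g | Camostat | Placebo | Difference (points) |
|---|---|---|---|---|
| 25% | 0 | 22.5/192.5 = 11.7% | 22.5/92.5 = 24.3% | -12.6 |
| 50% | 0 | 15/185 = 8.1% | 15/85 = 17.6% | -9.5 |
| 75% | 0 | 7.5/177.5 = 4.2% | 7.5/77.5 = 9.7% | -5.5 |
| 25% | 10% | 22.5/175.5 = 12.8% | 22.5/85.5 = 26.3% | -13.5 |
| 50% | 10% | 15/168 = 8.9% | 15/78 = 19.2% | -10.3 |
| 75% | 10% | 7.5/160.5 = 4.7% | 7.5/70.5 = 10.6% | -6.0 |
| 25% | 20% | 22.5/158.5 = 14.2% | 22.5/78.5 = 28.7% | -14.5 |
| 25% | 25% | 22.5/150 = 15.0% | 22.5/75 = 30.0% | -15.0 |

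With g = 0 the risk ratio moves only from 0.50 to 0.48, 0.46 and 0.44.

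**Keeping all event subjects instead (f = 0).**
- g = 10%: 30/183 = 16.4% vs 30/93 = 32.3%, difference -15.9.
- g = 20%: 30/166 = 18.1% vs 30/86 = 34.9%, difference -16.8.
- g = 25%: 30/157.5 = 19.0% vs 30/82.5 = 36.4%, difference -17.3.

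**No true effect (20% in both arms, 40 and 20 events, g = 0).** Equal f = 50% gives 20/180 = 10/90 = 11.1%, difference 0. With f = 25% in camostat and 50% in placebo the result is 30/190 = 15.8% vs 10/90 = 11.1%, a false 4.7 points. Reversing the shares reverses the sign.

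**The case against.** The case for leaving the rules alone is substantial.

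- **No primary conclusion rests on PP1 or PP2.** This stands.
- **The mechanism is mostly assumed.** A reader might infer that hospitalized or ER subjects as a group drop out of the PP sets. The documents do not support that: nothing requires dosing to stop at hospitalization or an ER visit, and an ER visit alone is compatible with 14 full days. This stands; only death during dosing is a certain route.
- **That route may be empty.** The draft fever table shell (Table 14.2.3) carries a note that no subject died on or before Day 14. It may be template text and cannot be relied on, but early deaths may well be few.
- **A false treatment effect is not shown.** A reader might infer one from the table above. It needs exclusion shares that differ by arm, and the documents give no reason for that in a blinded trial. With equal shares the risk difference shrinks, or is unchanged when g = f.
- **Exempting event subjects outright is not clearly better.** At f = 25% and g = 20% the current rule gives -14.5 and the exempting rule -16.8, against a true -15.0. This stands, and it rules out simply replacing the current sets.
- **Bottles should come back.** Protocol 9.5 requires return at the end of treatment, so non-return should be uncommon, and the rule tends to keep early-event subjects in PP2. That limits how often the rule matters but does not make the recorded value right.
- **A primary event hardly confounds its own assessment.** That is the sensible reading of the PP2 intercurrent-event clause, but the clause is a judgment call and one sentence would settle it.

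**Conclusion.** The point holds in a limited form, for supportive analyses only.

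Two parts need no assumption about f or g. First, reading 14-day completion plainly, a death during dosing puts the subject outside PP1, so PP1 survival to Day 15 is conditioned on its own outcome. Second, scoring an unreturned bottle as 112 tablets is wrong as written for anyone who stopped early, and it can make PP2 membership turn on bottle return.

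The wider effect on PP event rates is conditional. Rates are understated only where f exceeds g. Over the assumed range the difference falls between -15.0 (g = f) and -5.5 points (f = 75%, g = 0), and the documents do not say where in that range the trial would lie. ITT and the sample size are untouched.

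**What to change.** 1. **Unreturned bottle (SAP 2.5.2, 4.3.8 and the under-80% row of Table 1).** Use eDiary dose counts. If neither source exists, treat compliance as unknown and state whether such subjects are in or out of each PP set. Note that eDiary counts are self-reported.
2. **PP2 (SAP 2.5.3).** State that a primary event is not itself an excluding intercurrent event.
3. **Additional PP version, alongside the current one.** Compute compliance as tablets taken over tablets due up to the earlier of the primary event or the end of treatment, with no completion requirement after an event. State its own tilt: it enlarges the difference as non-event exclusions grow (-15.9 at g = 10%, -17.3 at g = 25%, true value -15.0). Showing both versions lets the reader see how much the choice matters.
4. **Reporting.** Tabulate PP1 and PP2 exclusions by arm and by event status, and do not interpret PP1 survival as an efficacy result.

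The cost is SAP wording, one derivation from eDiary and End of Study data already collected, and a few extra tables. Trial conduct and the ITT analysis do not change.
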